2.1.2 Clinical Experience

[¹¹C]MRB can be used to image NET-rich regions in the body at rest. Using a rodent model, [¹¹C]MRB PET imaging has been shown to appropriately 1) identify NET-rich regions in the body including BAT, heart, liver, pancreas, and kidney, 2) NET could be used as a highly specific target for BAT, and 3) that BAT can be detected in rodents under both room temperature and cold conditions ²⁴. Furthermore, the binding of [¹¹C]MRB in BAT was completely abolished by the pretreatment with a NET inhibitor, demonstrating the specific binding of the proposed ligand to BAT ²⁴. Building upon those rodent studies, the use of [¹¹C]MRB for imaging human BAT was validated under both cold and room temperature (RT) conditions at rest ¹². Ten healthy, Caucasian subjects (5M/5F: age 25±3, BMI 22±3 kg/m²)

HIC 2000030749

underwent [¹¹C]MRB PET-CT imaging for cervical/supraclavicular BAT under RT and cold-stimulated conditions (RPCM Cool vest; enthalpy 15°C) compared to ¹⁸F-FDG PET-CT imaging. Uptake of [¹¹C]MRB, was quantified as the distribution volume ratio (DVR). As seen in Figure 1, BAT [¹¹C]MRB binding was similar under both RT and cold conditions (BAT DVR: RT 1.0±0.3 vs. cold 1.1±0.3, $p=0.31$). Importantly, BAT DVR [¹¹C]MRB at RT correlated positively with body temperature ($r=0.92$, $p=0.004$).

Figure 1. A) Representative subject during scanning at RT and cold; B) [¹¹C]MRB Distribution Volume Ratio (DVR) in all subjects at RT and cold, closed marker = female

Obesity is associated with marked decrease in [¹¹C]MRB binding of human BAT. Recently, we have shown that there is a marked difference in [¹¹C]MRB binding of BAT amongst obese compared to lean women ² (Figure 2). In this proof of concept study, 15 healthy, non-diabetic Caucasian women (9 lean, age 25.6 ± 1.7, BMI 21.8 ± 1.3 kg/m² and 6 obese age 30.8 ± 8.8 BMI 37.9 ± 6.6 kg/m²) underwent PET-CT imaging of the neck/supraclavicular region using [¹¹C]MRB under RT conditions. We observed that [¹¹C]MRB binding was reduced in women with obesity in comparison to the lean group suggestive of decreased BAT. However, it remains to be determined whether NET in BAT is also reduced in men with obesity.

[figure not shown]
Figure 2. Decreased [¹¹C]MRB binding in BAT in women with obesity. A) Two representative subjects; B) All subjects.

Lean female participant

[figure not shown]

Fig. 3a

Muscle DVR v BMI

Obese female participant

Obesity is associated with altered [¹¹C]MRB binding

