Body Composition, Percent Body Fat & Percent Body Water: will be assessed using bioelectrical impedance analysis Tanita® scale (FDA cleared); which is a special multi frequency segmental body composition analyzer that delivers a very mild electrical current through the feet that allows measurement of fat mass, percent body fat, fat free mass, total body water, and percent body water. This test will be performed at screening visit. For better accuracy, measurement of percent fat and percent body water will be obtained with whole body Dual X-Ray Absorptiometry (DXA) scan (Hologic®) (located in the HRU) on screening-OGTT visit. The scanner arm will move over the participant's body from feet to head. The machine uses a small amount of radiation (one tenth of the amount of radiation from a chest x-ray) to measure body fat, muscle and bone density.

Subjects who fail any of the screening procedures will be informed and excluded from participating in the study, however they will be allowed to be re-screened at a later time,

Visit 2 – Whole body PET Imaging Visit - FASTING:

Two weeks after the screening visit, participants who qualified for the study will be asked to come to the PET Center to undergo the whole body [11C]MRB PET scan. Participants will be asked to maintain their regular exercise routine.

Human PET-CT Protocol: [11C]MRB will be synthesized at the Yale PET center based on procedures described and previously performed 1,2. An intravenous bolus dose of MRB (~120mCi) will be injected by an infusion pump. PET data will be acquired dynamically for 120 min using the Siemens mCT-X whole-body PET/CT scanner using continuous bed motion to image perform multiple PET bed acquisitions from the top of the head to the lower abdominal region. A CT scan will be performed for attenuation correction and to help delineate the BAT and other regions of interest (ROIs). Images will be reconstructed with an ordered subset expectation maximization algorithm using point spread function correction and time-of-flight information. To delineate fat (WAT, BAT) and skeletal muscle regions of interests (ROIs),

HIC 2000030749

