CT images are first resliced to match the resolution and location of PET images. As performed in previous studies 2, a supraclavicular ROI is first manually drawn on the CT images. Within that area, the fat ROI is segmented using the CT images and an intensity window from -200 to -50 HU. Subsequently the fat ROI is segmented into WAT and BAT ROIs by using the ¹¹C-MRB PET images: Standardized Uptake Value (SUV) ≥ 1.25 for BAT, SUV < 1.25 for WAT.

Brain ROIs for predetermined NET-rich areas of the brain, including the locus ceruleus, raphe, thalamus and hypothalamus were defined in template space and are applied to the PET images by using the participant's MR image as an intermediate step. For analysis of tracer uptake, mean SUV will be reported for segmentation of adipose tissue. Because the distribution volume ratio (DVR) is a more precise measurement of uptake for reversible tracers ³ such as ¹¹C-MRB, regional quantification of ¹¹C-MRB uptake as DVR (V_T / V_{ND}), estimated via multilinear reference tissue model 2 (MRTM2) ^{4,5} ($t^* = 30$ min) using the occipital cortex, a region with low NET density ^{2,5,6} as the reference region. MRTM2 reduces the variability of MRTM (4) parameter estimates by fixing one of the three parameters, the parameter k_2' , which is only related to the reference region time-activity curve, to a common value for all target regions. In this study, the parameter k_2' was fixed to 0.021 min⁻¹, based on previous brain studies and previous BAT PET studies ². In addition to DVR, MRTM2 can estimate R_1 , the relative radioligand delivery, using a 1 tissue compartment model (1TC). For the 1TC model, volume of distribution, $V_T = K_1/k_2$, where K_1 (mL/min⁻¹/mL⁻¹) is the rate constant of radiotracer from plasma to tissue of target organ and k_2 is the rate constant from tissue to plasma. Using a reference region with non-displaceable binding (e.g. occipital lobe) we can estimate similar rate constants: $V_{ND} = K'_1/k'_2$. Recalling that K_1 and K'_1 are the rate constants for transfer from plasma to the tissue and reference region, respectively, then we can estimate relative radioligand delivery as $R_1 = K_1/K'_1$.

The maximum number of attempts for each failed/incomplete imaging and test is 2 times.

Visit 3 – Whole body PET Imaging Visit - High-Carbohydrate Mixed Meal Test (MMT)

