5.3.2 Eligibility Criteria/Vulnerable Populations

Inclusion Criteria:

HIC 2000030749

In order to be eligible to participate in this study, an individual must meet all of the following criteria:

1. Provision of signed and dated informed consent form
2. Stated willingness to comply with all study procedures and availability for the duration of the study
3. Age 18–45 years
4. In good general health as evidenced by medical history and lean (BMI 18.5-24.9 kg/m²) or non-diabetic obese (BMI 30-50 kg/m²) with a fasting plasma glucose (FPG) <100 mg/dL and a hemoglobin A1c <5.7%.

Exclusion Criteria:

An individual who meets any of the following criteria will be excluded from participation in this study:

1. Hypertension
2. Cardiac or pulmonary disease
3. Known history of Type 1 or Type 2 diabetes
4. Hepatic disease, swallowing and gastrointestinal disorders, including but not limited to diverticulitis and inflammatory bowel disease
5. Disorders or impairment of the gag reflux
6. Subjects with previous gastrointestinal surgery.
7. Subjects with a pacemaker or other implanted electro medical device
8. Current use of anti-obesity medications, supplements and/or anti-hyperglycemic medications
9. Neurological injury or illness, and psychiatric medications
10. Women who are pregnant or lactating
11. Subjects who suffer from claustrophobia
12. Subjects who have received a diagnostic or therapeutic radiopharmaceutical within 7 days prior to participation in this study
13. Subjects who work with radiation or have participated in other research studies involving ionizing radiation within one year of the PET scans that would cause the subject to exceed the yearly dose limits.
14. Subjects with history of IV drug use which would prevent venous access for PET tracer injection
15. Severe motor problems that prevent the subject from lying still for PET and MR imaging
16. Subjects who complain of chronic pain
17. Blood donation within 8 weeks of the study
18. Non-English speaking subjects
19. Subjects with poor venous access
20. Subjects with an allergy or intolerance to the carbohydrate meal or IV contrast.
21. Subjects with a history of bleeding disorders

HIC 2000030749

- 22. Subjects on anticoagulation medications.
- 23. Subjects who are Transgender

6 Methods

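### One fixed SUV cut-off separates BAT from WAT in groups chosen to differ in body size; if SUV is scaled to body weight, part of a lean-obese adipose DVR difference could come from the segmentation

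*Combined protocol and SAP*

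**What the plan says.** The image-analysis text in 5.1, repeated in the Synopsis and in 6.3, has three steps. First, "a supraclavicular ROI is first manually drawn on the CT images". Second, fat is selected within that area by a CT window of -200 to -50 HU. Third, that fat is split on the PET image: "Standardized Uptake Value (SUV) ≥ 1.25 for BAT, SUV < 1.25 for WAT". SUV serves to define the regions ("mean SUV will be reported for segmentation of adipose tissue"). Binding is quantified as DVR "using the occipital cortex, a region with low NET density".

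The groups are "lean (BMI 18.5-24.9 kg/m²) or non-diabetic obese (BMI 30-50 kg/m²" (5.3.2). Group differences in BAT and WAT binding are primary outcomes (5.2, 6.4.1).

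No section names the SUV normaliser. The only model factors named are group, sex and their interactions (6.5.1). Subsets and Covariates (6.5.9) is marked not applicable, and no sensitivity analysis on the cut-off is planned. Body composition is measured at screening, including DXA: "measurement of percent fat and percent body water will be obtained with whole body Dual X-Ray Absorptiometry (DXA) scan". It is not used in the segmentation.

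**The concern.** DVR is a ratio to a reference region and does not depend on body weight. The choice of voxels averaged into the BAT or WAT figure can. A weight-based SUV multiplies tissue concentration per injected dose by body weight. If extra fat mass takes up less tracer per kg than lean tissue, it adds weight without diluting the tracer in proportion, so the SUV of a given tissue rises. A fixed 1.25 then admits lower-DVR voxels to the BAT region. Those same voxels were the highest in the WAT region, so both averages fall. A difference between lean and obese participants could then appear in two primary endpoints with identical NET. Nothing in the plan would separate that from a real reduction.

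**Working it through.** **Inputs from the documents.** Cut-off SUV 1.25 (5.1, 6.3). Pilot BAT DVR 1.15 ± 0.19 lean vs 0.80 ± 0.12 obese, two-sided t-test (6.4.2). Pilot groups: "BMI 21.8 ± 1.3 kg/m² and 6 obese age 30.8 ± 8.8 BMI 37.9 ± 6.6 kg/m²" (2.1.2).

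**Inputs assumed, because the documents give none.** SUV is normalised to total body weight. Body fat p is 25% lean and 42% obese. Uptake per kg of fat relative to lean tissue, f, runs from 0 to 1. Voxel DVR is lognormal with mean 0.8 and CV 20-40%, the same in both groups. In lean participants SUV 1.25 corresponds to a DVR cut-off of 0.80-0.95. Alpha is 0.05.

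**1. The plan's own figure.** Pooled SD = √((0.19² + 0.12²)/2) = 0.159, so d = 0.35/0.159 = 2.20. Exact t-test power is about 93% with 6 per group and 86% with 5. The plan's sample sizes reproduce, and 0.35 is the yardstick below.

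**2. Cut-off per injected dose.** This is 1.25/weight. At the pilot mean BMIs and equal height the weight ratio is 37.9/21.8 = 1.74, so the cut-off is 1 - 21.8/37.9 = 42.5% lower in the obese group. Most of this is ordinary dilution in a larger body, so it is not the bias. The bias is what remains after dilution (step 3).

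**3. SUV inflation.** If injected activity is shared between lean mass and fat mass weighted by f, the SUV of a given tissue is proportional to 1/(1 - p + f·p). The obese/lean ratio is r = (0.75 + 0.25f)/(0.58 + 0.42f).

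**4. Effect on mean DVR.** The lean group averages voxels above cut-off c, the obese group voxels above c/r. With σ² = ln(1 + CV²) and μ = ln(0.8) - σ²/2, the mean above c is 0.8·Φ((μ + σ² - ln c)/σ)/Φ((μ - ln c)/σ). The WAT mean is the corresponding mean below c.

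One case: CV 30%, c = 0.90, f = 0.5. Then r = 0.875/0.79 = 1.108 and c/r = 0.813. Mean BAT DVR is 1.10 lean and 1.02 obese (difference -0.07 before rounding); mean WAT DVR is 0.68 and 0.64.

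Over all assumed CVs and cut-offs, the spurious obese-minus-lean differences are:

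| f | r | BAT DVR | WAT DVR |
|---|---|---|---|
| 0 | 1.293 | -0.19 to -0.11 | -0.12 to -0.09 |
| 0.3 | 1.169 | -0.12 to -0.08 | -0.07 to -0.06 |
| 0.5 | 1.108 | -0.08 to -0.05 | -0.05 to -0.04 |
| 0.8 | 1.037 | -0.03 to -0.02 | -0.02 to -0.01 |
| 1 | 1 | 0 | 0 |

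**5. A wider set of assumptions.** Take median voxel DVR 0.6-1.0, log-SD 0.3-0.5 and lean reference-region SUV 1.1-1.6. An obese/lean reference-SUV ratio of 1.1 gives -0.11 to -0.04. With between-person SD 0.159 and 10 vs 10 participants, the chance of a significant t-test is then 8-30% instead of 5%. At a ratio of 0.9 the sign reverses, to +0.05 to +0.13.

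**6. Would a lean-mass SUV cure it?** It multiplies r by 0.58/0.75. The ratio becomes 1.00, 0.904, 0.857 and 0.802 at f = 0, 0.3, 0.5 and 0.8. The spurious BAT difference becomes 0, +0.07 to +0.10, +0.11 to +0.15, and +0.17 to +0.23. It is exact only at f = 0. From roughly f = 0.4 upward its error exceeds that of body-weight SUV, in the opposite direction.

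**The case against.** The size rests on assumption throughout. The protocol gives no normaliser, no relative fat uptake, no voxel DVR distribution and no reference-region SUV by group. If SUV is already normalised to lean mass, the mechanism as described largely disappears. If tracer concentration falls in proportion to weight there is no bias, and the direction is not guaranteed. Keeping the pilot's region method also has real value for comparability. All of this stands. It limits the point to what the segmentation can do and makes the magnitude a range.

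Three stronger readings are tempting and unsupported. A reader might take the roughly 40% lower absolute cut-off in heavier people as the bias, but most of it is the dilution that SUV is designed to allow for. A reader might infer that the pilot's 1.15 vs 0.80 is an artefact. No figure in the documents shows that, and the modelled effect at 25% vs 42% body fat is smaller than 0.35. A reader might conclude that DXA lean mass should replace body weight as the main normaliser. Step 6 shows that this over-corrects unless fat uptake is near zero, and it could hide a true reduction.

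What the objection does not answer is that the plan, as written, gives no means of checking whether the adipose result depends on body size.

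**Conclusion.** The concern holds as a conditional one. The fixed SUV 1.25 rule and the absence of any check on it are explicit. Under total-body-weight SUV and fat uptake below that of lean tissue (both assumed), the rule can lower mean BAT and WAT DVR in obesity with no NET difference. For 25% vs 42% body fat and relative fat uptake of 0 to 0.8, the spurious BAT DVR difference is about -0.19 to -0.02. That is roughly 54% to 6% of the design difference (0.19/0.35 and 0.02/0.35). It is zero with no inflation and positive if reference-region SUV is lower in obesity. The point is confined to the two adipose endpoints; muscle DVR, brain DVR and MSNA are untouched. It bears on how an adipose group difference may be interpreted and does not invalidate the design.

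**What to change.** In 5.1 and 6.3 (and the matching Synopsis text):

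- State the SUV normaliser.
- Keep the SUV 1.25 segmentation for comparability with the pilot.
- Pre-specify, before any group comparison, a weight-independent analysis reported beside it. This can be DVR over the whole CT-defined supraclavicular fat region (-200 to -50 HU), BAT/WAT segmentation by a fixed ratio to the occipital reference region, or both. In the model above, either gives a spurious difference of zero whatever the weight ratio.
- A lean-mass SUV using the Visit 1 DXA may be added as a bracketing sensitivity analysis. It should not be primary.
- State the reading in advance: if the adipose difference appears only under SUV 1.25, report that it may partly reflect body-size-dependent segmentation, and do not attribute it to NET alone.

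The cost is some re-analysis of images and body-composition data that the protocol already collects. Whole-fat DVR mixes BAT and WAT, so it is less specific to BAT. A ratio cut-off removes the dependence on body size but still selects voxels on a quantity close to the outcome.

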In humans, *in vivo* quantification of NET levels can be measured using a selective positron emission tomography (PET) radioligand for NET, (S,S)-¹¹C-O-methylreboxetine ([¹¹C]MRB) ^{23,24}, and our group has shown that [¹¹C]MRB can measure NET in multiple tissues including brown (BAT) and white adipose tissue (WAT), skeletal muscle, and brain ^{12,25}. Furthermore, our preliminary data using [¹¹C]MRB scanning in healthy lean individuals as well as individuals with obesity suggest that obesity is associated with marked differences in NET availability in BAT ² as well as the brain ²⁶. Use of PET allows us to assess NET binding in multiple tissues simultaneously. In these proposed studies, we will use NET-binding to investigate the role of SNS dysfunction in healthy men and women with obesity. Furthermore, because there is strong evidence that food induced SNS activity increment is blunted in individuals with obesity ^{15,27,28}, we will also test the impact of obesity on response to a relevant stimulus (food). Our overall premise is that **coordinated multi-organ response (brown and white adipose tissue, muscle, liver, pancreas) is modulated by the SNS both in the fasting state and after a meal; however, this coordinated response becomes dysfunctional in obesity**. Therefore, to better understand the potential for dysregulated coordination of the SNS in obesity, we will synchronously measure SNS activation of a) peripheral tissues: adipose tissue (BAT and WAT) and skeletal muscle; and b) CNS by using [¹¹C]MRB whole body PET imaging in combination with muscle SNS activity (MSNA) during rest both in the fasting state and after a meal.

[figure not shown]

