Human obesity is associated with altered brain NET. Central noradrenergic neuronal dysfunction has been observed in obesity ^{26,31-33}. Li et al ²⁶ demonstrated that obese subjects have decreased NET-availability in the thalamus (a sensory relay region in the brain); although these findings were not confirmed in a European cohort ³⁴. Vettermann et al ³⁵ showed that NET activity in the insula and hippocampus predicts successful weight loss. Furthermore, NET inhibitors used for the treatment of attention deficit disorder (ADHD) can promote weight loss ^{36,37}. In a prior study from our group ²⁵, we observed that NET in the hypothalamus correlated with counterregulatory hormonal and metabolic response to hypoglycemia (a stimulus to induce stress response

and increase hunger) ²⁵ (Figure 6). However, it is not clear whether NET- rich regions in the CNS,

HIC 2000030749

[figure not shown]
such as hypothalamus, thalamus, and brain stem (areas involved with glucose metabolism and autonomic function) are important in regulating SNS activation of target organs. We plan to investigate the relationship between CNS NET-availability and peripheral NET (measured by whole-body ($[^{11}\text{C}]$ MRB PET imaging) and SNS activity (measured by MSNA) both in normal BMI and obese individuals. We propose that CNS NET-availability at rest in the fasting state in the hypothalamus and thalamus (brain regions involved with glucose and energy metabolism) will correlate with NET binding in BAT and skeletal muscle in individuals with normal BMI. In contrast, because of obesity-associated regionalized SNS dysfunction, CNS-NET availability will not correlate with peripheral NET-binding or MSNA in individuals with obesity.

High carbohydrate meal ingestion is a strong stimulus for activation of the SNS. Food intake (in particular carbohydrate-rich meals) is a strong stimulus for activation of SNS in both animals³⁸ and humans³⁹⁻⁴². This has been demonstrated by plasma NE tracer kinetics^{38,39} and MSNA^{39,41-43}. In rodents, NE turnover in BAT, but not in the spleen or heart, increased in response to a meal³⁸. Regionalized SNS activation was also observed in humans: increased in skeletal muscle and kidneys, but no or minimal change in heart and liver³⁹. SNS play a major role in activating BAT after a meal⁴⁴, and a recent study using PET Imaging showed increased BAT activation after ingestion of a high carbohydrate-rich meal⁴⁵.

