4.3 Secondary Objectives (if applicable)

The secondary objectives of this study are: 1) to evaluate whether gender differences affect peripheral SNS in healthy normal weight and obese men and women in adipose tissue (WAT and BAT) and muscle (resting/fasting); 2) To investigate the relationship between peripheral and central SNS activity in obesity, by correlating SNS activity in peripheral tissues (WAT, BAT, and muscle) and brain; and 3) To investigate NET CNS and peripheral SNS activity before and after a high carbohydrate mixed meal in lean and obese men and women.

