6.4 Statistical Method

6.4.1 Statistical Design

Primary endpoints: Group differences in 1) [¹¹C]MRB-binding in brown adipose tissue (BAT), white adipose tissue (WAT), skeletal muscle, and norepinephrine-rich brain regions (hypothalamus and thalamus); and 2) microneurography (muscle sympathetic nerve activity (MSNA)). Correlations between NET in the brain and peripheral NET and MSNA.

Secondary endpoints: Plasma hormone levels, heart rate, blood pressure, electrocardiogram (beat-to-beat)..

Statistical Analysis: Before statistical testing, all continuous variables will be tested for normality of distribution. Summary statistics will be computed. For between-group comparisons of patient characteristics, two sample t-test or Mann-Whitney U test will be used for continuous variables, and Fisher's exact test for categorical variables. Comparisons of repeatedly measured MSNA will be made using the mixed model analysis. Fixed factors include group and sex and their interactions. Linear contrasts comparing differences between groups or different time points within a group will be estimated.

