6.4.2 Sample Size Considerations

Statistical Considerations: sample sizes of 6 per group (normal BMI x obesity, and women x men) will achieve 90% power to detect a between-group difference. To account for up to 10% missing data due to drop out or poor-quality data, we will need to enroll a total of 40 subjects (10 per group) for this study.

Fasting: A Power analysis was performed based on previous study published from our group in lean and obese female individuals: (lean 1.15 ± 0.19 vs obese 0.80 ± 0.12 BAT DVR, $p = 0.004$; two-sided independent sample t-test)². In our previous cross-sectional comparison,

HIC 2000030749

using the mean and standard deviations between lean and obese individuals, we expect an effect size of $d=2.20$ and with a power of 0.90, to account for possible smaller differences in males, we need 6 individuals per group. For reference, $d=2.20$ and 0.80 power would be 5 per group.

MMT: Postprandial whole-body energy expenditure per fat free mass (FFM) differences were shown for low-BAT (32 ± 2 kcal/day/kg FFM) and high-BAT (37 ± 2 kcal/day/kg FFM)⁴⁵. Based on these data, we can calculate an effect size of $d=2.50$. With a power of 0.80 required, we will need 8 individuals (4 per group) determine EE differences between low- and high-BAT individuals. Increasing the power to 0.95 will increase the number of individuals to 12 (6 per group). Due to the technical challenges of performing microneurography on multiple occasions in obese women, we overestimate and account for $\sim 10\%$ failure rate, so we will recruit 10 subjects per group.

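### Brain and peripheral DVR share one occipital reference from the same scan, so the planned brain–periphery correlations may carry a reference component of unknown size and sign that the plan does not check

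*Combined protocol and SAP*

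**What the plan says.** Brain and periphery are imaged in one whole-body acquisition; section 2.1.1 notes that "Use of PET allows us to assess NET binding in multiple tissues simultaneously". Section 5.1, repeated in the synopsis and section 6.3, quantifies regional uptake as DVR by MRTM2 "using the occipital cortex, a region with low NET density". The reference-region parameter k2' is fixed "to a common value for all target regions". No other reference is named. BAT and muscle are reported as DVR in section 2.1.2, and the fasting power calculation uses BAT DVR. SUV appears only in connection with segmenting the fat.

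Section 6.4.1 places "Correlations between NET in the brain and peripheral NET and MSNA" with the primary endpoints. Section 4.3 has the brain–periphery relationship as a secondary objective, to be studied "by correlating SNS activity in peripheral tissues (WAT, BAT, and muscle) and brain". Section 2.1.2 predicts that NET availability in the hypothalamus and thalamus "will correlate with NET binding in BAT and skeletal muscle in individuals with normal BMI", and that "CNS-NET availability will not correlate with peripheral NET-binding or MSNA in individuals with obesity". It gives no sign for the predicted lean-group correlation.

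No correlation method is specified. Section 6.5.2 restates the objectives without an analysis, covariates are marked not applicable in section 6.5.9, and no check of occipital uptake is planned. Section 6.3.5 lists an arterial line on PET days, but no arterial-input analysis is described.

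**The concern.** If one participant's occipital estimate is too low for reasons unrelated to the target tissues, that participant's brain DVR and BAT, WAT and muscle DVRs all rise together. Across participants this produces a correlation between brain and periphery even when the tissues are unrelated. The plan would interpret a lean-group correlation as coordinated sympathetic regulation and has no analysis to separate that from a property of the shared reference. Since the correlation is listed with the primary endpoints, a central claim of the study could rest partly on the reference.

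**Working it through.** **The plan's own figure.** The documents give no figure for the correlations. The BAT data used below come from section 6.4.2 ("lean 1.15 ± 0.19 vs obese 0.80 ± 0.12 BAT DVR"), where the stated effect size reproduces: d = (1.15 − 0.80)/√((0.19² + 0.12²)/2) = 0.35/0.159 = 2.20. With the noncentral t and an assumed two-sided alpha of 0.05, n = 5.51, rounded up to 6 per group, at 90% power, and 4.44, rounded up to 5, at 80%. Both match. This confirms the inputs but says nothing about the correlations.

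**Inputs.**
- BAT DVR CV, lean: 0.19/1.15 = 0.165; obese: 0.12/0.80 = 0.150 (section 6.4.2).
- n = 20 per BMI group (section 5.3.1).
- Brain DVR CV: not given; assumed 12%, and 15% as an alternative.
- CV of the error in the occipital estimate (CVref): not given; assumed 3 to 9%, taken to 10% with brain CV 15%.

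**Formula.** To first order, treat each log DVR as a tissue term minus the same log reference error, with all three terms independent. The covariance is then the variance of the reference error, so

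r ≈ CVref² / (CVbrain × CVperiphery).

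For brain CV 12% the denominator is 0.12 × 0.165 = 0.0198. At n = 20 the critical |r| is 2.101/√(18 + 2.101²) = 0.444.

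| CVref | r, formula | r, simulated | Share with p < 0.05 | Share of brain DVR variance due to reference error (CVref²/0.12²) |
|---|---|---|---|---|
| 3% | 0.0009/0.0198 = 0.045 | 0.04 | 6% | 6% |
| 5% | 0.0025/0.0198 = 0.126 | 0.12 | 8% | 17% |
| 7% | 0.0049/0.0198 = 0.247 | 0.24 | 19% | 34% |
| 9% | 0.0081/0.0198 = 0.409 | 0.40 | 45% | 56% |

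With brain CV 15%, CVref of 5, 8 and 10% gives simulated r of 0.10, 0.25 and 0.39 and false-positive rates of 7.0, 19.4 and 43.4%. The variance shares are 0.05²/0.15² = 11%, 0.08²/0.15² = 28% and 0.10²/0.15² = 44%. At CVref 9% the formula gives 0.0081/(0.15 × 0.165) = 0.33, with a share of 36%.

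**Sign.** The formula needs reference error that is independent of the tissue terms. Two other sources of occipital variation behave differently:
- True non-displaceable uptake. Brain V_T contains V_ND as a factor, so it cancels in brain DVR. Simulated r was 0.00 with V_ND CVs of 10 to 20% and no reference error.
- Residual NET binding in the occipital cortex that tracks brain binding. It raises the brain numerator more than the denominator but lowers peripheral DVR. With occipital binding at 10 to 30% of thalamic binding (assumed binding values) and no error, r was −0.12 to −0.30. Adding 5% error brought it to 0.01 to 0.08.

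**Both groups.** At brain CV 15%, the obese group gets r of about 0.11 at CVref 5% and 0.44 at 10%, slightly more than the lean group because its BAT CV is lower. A direct lean-versus-obese comparison of correlations (Fisher z) stays near nominal, at 5.2 to 5.5%. If the groups are only tested separately, a significant positive lean correlation with a non-significant obese one arises by chance in 2.4% of trials without reference error, and in 5.7, 15.2 and 20.9% at CVref 5, 8 and 10%.

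**Effect of a remedy.** With the peripheral measure not divided by the occipital reference (brain CV 15%), false-positive rates at CVref 2, 5, 8 and 10% were 5.0, 4.8, 5.0 and 5.0%.

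**The case against.** The strongest reply is that this shows a possibility and not a bias. Neither CV that drives the result is in the documents, and the BAT CV comes from a small sample (9 lean women). At CVref 3 to 5% the error rate is 6 to 8%, close to nominal. The 45% figure requires more than half of all between-person brain DVR variance to be reference error, which nothing in the documents supports. This stands: the size is unknown and may be negligible.

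A reader might go further and infer that a positive artefact is built into these correlations and reproduces the lean-group prediction. The documents do not support that. The sign depends on which source of occipital variation dominates. Section 2.1.2 states no sign. The component acts equally in obese participants, where it works against the predicted absence of correlation. A direct test of the group difference would be nearly immune, although the plan does not specify one, and separate within-group tests are exposed.

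It is also fair to say that the endpoint includes correlations of brain NET with MSNA, and that section 2.1.2 plans correlations of NET with heart rate variability and catecholamines. In none of these are both variables divided by occipital uptake. They are useful context, but they do not test the brain–periphery NET correlation itself.

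Finally, section 5.1 chose DVR for its precision. A blood-pool ratio is less precise and less validated, and no metabolite correction is described. That argues against replacing DVR, not against a sensitivity check.

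**Conclusion.** The concern holds in conditional form. The shared reference, the planned correlation and the absence of any safeguard are all in the documents. The brain–periphery NET correlations may therefore contain a shared-reference component, positive if reference error dominates and possibly negative if residual occipital binding tracks brain binding. Its size cannot be derived from the documents. Across the assumed range it runs from negligible to r of about 0.40 and a false-positive rate of about 45% at n = 20. Reaching CVref 9% means that reference error makes up 36% (brain CV 15%) to 56% (brain CV 12%) of brain DVR variance. Brain–MSNA correlations are unaffected. Because neither size nor sign is known, a brain–periphery correlation in either group cannot be read as coordination, nor its absence as dysfunction, without a check. The check is inexpensive and should be pre-specified.

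**What to change.** Keep DVR as the planned measure and add three items to section 6.5.2:

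1. A pre-specified sensitivity analysis of the brain–periphery correlations in which the peripheral measure is not divided by occipital uptake. One example is BAT, WAT and muscle uptake relative to an image-derived blood pool from the same scan; the heart and aorta lie within the head-to-lower-abdomen field.
2. A report of occipital uptake by BMI group and by fasting or meal condition, to show whether the reference varies enough to matter.
3. A rule that a brain–periphery correlation is described as coordination only if the sensitivity analysis agrees in direction and is similar in size.

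Using the left occipital cortex for brain and the right for periphery would not be enough. Error common to both halves, such as head motion, remains. At CVref 7%, brain CV 12% and an assumed between-hemisphere error correlation of 0.8, the spurious r falls only from 0.25 to 0.8 × 0.25 = 0.20.

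The cost is one extra region drawn on images already acquired and a short addition to the analysis text, with no added burden for participants. The drawback is a peripheral ratio that is less precise and less validated than DVR, which is why it serves as a check and not a replacement.
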